6 HANDLING OF MISSING VALUES

Since this study analyses actual medical claims data which was reviewed by HIRA, no imputation for missing values will be performed.

7 STATISTICAL METHODOLOGY AND STATISTICAL ANALYSES

7.1 STATISTICAL METHODS

Means, medians, and standard deviations will be provided for continuous variables when performing descriptive analysis of continuous data. Numbers and percentages will be provided for dichotomous and polychotomous variables when performing descriptive analysis of categorical data. Bivariate comparisons of baseline characteristics and outcomes measures will be provided. Appropriate tests (e.g., t-test, chi-square test) will be used based on the distribution of the measure. The cumulative incidence rate for clinical outcomes (major bleeding event, and stroke) will be calculated. The incidence rate will be calculated as the number of patients who experience the event divided by the observed time at risk. An unadjusted Kaplan Meier curve will be drawn to illustrate time-to-event.

PFIZER CONFIDENTIAL

[figure not shown]
The propensity score matching (PSM) technique and the propensity score weighting technique will be used to control for confounders when comparing the antidepressants. After PSM, no significant differences are expected among all pre-index measures between the antidepressant cohorts except for clinical indication differences. Also covariates in Table 3 will be included in multivariate logistic regression framework for each antidepressant choice (binary variable of 1 for choice and 0 for no choice). Covariates will include variables such as age, geographic region, CCI score, and comorbidities. Non-pharmacologic treatments will be used as a covariate if dependent variable is adherence, persistence, or discontinuation since a previous study reported accompanying number of non-pharmacologic treatments significantly increase adherence of antidepressants (Ahn J et al., 2011). The final lists of variables to be used in the model will be discussed and determined during analysis development, after reviewing the pre-matched descriptive tables and post-matched pre-index measures. All data analysis will be executed using statistical software SAS version 9.4 or later.

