2.2 STUDY OBJECTIVES

Primary objectives:

1. Explore baseline characteristics and drug utilization patterns of 11 commonly used antidepressant therapy during 90 days of acute treatment phase
 - Top 11 commonly used antidepressants according to local market data are as follows:
 - Escitalopram, paroxetine, fluoxetine, mirtazapine, duloxetine, sertraline, venlafaxine, tianeptine, vortioxetine, desvenlafaxine, bupropion
 - Proportion of antidepressants prescribed by sex, age (<20, 21-64, > 65), sex and age combined
 - Initial doses used, average daily doses of each antidepressants
 - Average length of treatment with index medication before therapy change occurs (switching, combination, augmentation, discontinuation)
 - Adherence and persistence measured by medication possession ratio during first 90 days of treatment period
2. Explore drug utilization patterns such as therapy changes, medication compliance and recurrence relationship, and risk of adverse outcomes during maintenance phase
 - The choice of antidepressant, average length of new treatment maintenance, average number of co-administered medications (e.g., atypical antipsychotics, mood stabilizer, thyroid hormone, psychostimulant) when following changes occur from initial monotherapy:
 - Switching
 - Combination
 - Augmentation
 - Medication compliance and recurrence
 - Compliance measured as adherence and persistence
 - Recurrence
 - Relationship between recurrence and compliance

PFIZER CONFIDENTIAL

- *Risk of adverse outcomes measurement between individual ADs that are well known to be treatment-related (e.g., hyponatremia, GI bleeding, fractures, falls, risk of intracranial hemorrhage, attempted suicide/self-harm, myocardial infarction, epilepsy/seizures, stroke/transient ischemic stroke)*

Secondary objectives:

1. *Choice of antidepressants and drug utilization patterns in patients with various comorbidities*
 - *Psychiatric comorbidities*
 - *Mild cognitive impairment (MCI)*
2. *The relationship of non-pharmacologic treatment and discontinuation, medication compliance*
 - *Non-pharmacologic treatments may include: cognitive behavioral therapy (CBT), frequency of physician visit during acute and maintenance phase of treatment*
 - *Frequency of visit during the first 3 months of acute phase and its relationship to treatment maintenance at 4, 5, 6, 7, 8, 9 month time points and discontinuation rate*
3. *Choice of antidepressants by non-psychiatric specialty*

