Persistence	Primary outcome	HIRA Database	
For each of 11 study drugs, the average length of treatment on the index drug during the first 180 day period (allowing 14 day permissible gap) will be calculated
 
Switching, combination, augmentation, discontinuation will terminate the persistent period

Discontinuation	Primary outcome	HIRA Database	For each of 11 study drugs chosen as index drug, the percentage of discontinuation in the first 90 days from the index date (acute treatment phase) will be measured (allowing 14 day permissible gap)
Adherence	Primary outcome	HIRA Database	
For each of 11 study drugs chosen as index drug, adherence will be measured by MPR and persistence during the first 90 day and 180 day period from the index date, respectively (acute treatment phase). MPR ≥ 0.75 and persistence ≥ 90 will be considered as adherence.
 
* For those period with any identified adverse outcome such as GI bleeding will be considered as non-adherent period

Drug utilization pattern in acute phase	Secondary outcome	HIRA Database	
During the first 90 day period starting from the index date, the following types of drug utilization pattern is recorded
 
- monotherapy (kept on the index medication)- switching (switched to other antidepressant)- combination (adding other antidepressant)- augmentation (adding other non-AD drug such as antipsychotic)
Drug utilization pattern in maintenance phase	Secondary outcome	HIRA Database	
During the second 90 day period (91 ~ 180 days) starting from the index date, the following types of drug utilization pattern is recorded
 
- choice of antidepressant- monotherapy (kept on the same medication)- switching (switched to other antidepressant)- combination (adding other antidepressant)- augmentation (adding other non-AD drug such as antipsychotic)

PFIZER CONFIDENTIAL

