Comorbidities	Covariates	HIRA Database	
The following comorbidities which may affect the drug utilization patterns of antidepressants will be operationally defined using KCD-7 diagnosis codes in medical claims
 
 - Psychiatric comorbidities: panic disorder (F41.0), bipolar disorder (F31), PTSD (F43.1), acute stress (F43.0), personality disorder (F60-69), GAD (generalized anxiety disorder) (F41.1), adjustment disorder (F43.2), sleep disorder (F51), g470, f108), dementia (F00-F03, G30), OCD (obsessive compulsive disorder) ((F42), F429, F605, F428), substance related disorders (F10-19), schizophrenia (F20-29), eating disorder (F50), sexual dysfuntion (F52), mental retardation (F70-F79), developmental disorder (F80-F89), somatoform disorder F45, eating disorder F50 - Mild cognitive impairment (MCI): diagnosis code F06.7 along with a procedure code for neurocognitive function test FB001-FB060* - Charlson Comorbidity Index (CCI)
Non-pharmacologic treatments	Covariates	HIRA Database	
The following non-pharmacologic treatments which may affect antidepressant adherence and persistence/discontinuation will be defined using NHI procedure codes* in medical claims
 
 - Individual psychotherapy** NN012 intensive analytic NN013 intensive - Group psychotherapy NN021 general NN022 analytic NN023 psychodrama - Family psychotherapy NN031 individual NN032 group NN040 occupational or recreation therapy NN050 narcoticsynthesis - Electroconvulsive therapy NN071 simple ETC NN072 modified ETC - Continuous sleep treatment NN081 electro sleep treatment NN082 drug induced sleep treatment NN083 sleep treatment with anesthesia NN090 psychiatric rehabilitation NN100 psychiatric emergency treatment - Psychiatric social work NN111 individual history taking NN112 social work guidance NN113 social investigation

PFIZER CONFIDENTIAL

			
NN114 home visiting
 
* Since January 2018, new code system was employed for psychotherapy and expert advisor consensus will be used to align the new codes to the codes above
 
NN001-NN005 individual psychotherapy
 
NN061 Cognitive Behavioral Therapy-Individual
 
NN062 Cognitive Behavioral Therapy-Group
 
** NN011 supportive was excluded since it is more of a routine code used for majority of patients according to Ahn et al. (2012)¹³

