7.2.4 Relationship between Non-pharmacological Treatments and Antidepressant Compliance Analysis

- To understand the relationship between non-pharmacological treatments and antidepressant compliance among Korean patients with depression
- Secondary analysis
- Endpoints:
 - Medication compliance (adherence, discontinuation, and persistence) by the number of non-pharmacological treatments
- Population: patients who satisfy the acute treatment phase population
- Significance on continuous variables will be tested by ANOVA (if equal variance condition satisfied) or the Kruskal-Wallis H test (otherwise).
- Covariates: antidepressant class covariates such as SSRIs, SNRIs, and other ADs will be used as grouping variables.
- Missing values will be dropped from the analysis.
- The role of this analysis is to provide information on the relationship between non-pharmacological treatments and antidepressant compliance among Korean patients with depression.

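### SAP 7.1 adjusts adherence, persistence and discontinuation for non-pharmacologic treatments with no measurement window; if the count is post-index and enters a between-drug model, it attenuates drug differences and can create false ones

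*SAP*

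**What the plan says.** SAP 7.1, in the paragraph on controlling confounding when antidepressants are compared, says: "Non-pharmacologic treatments will be used as a covariate if dependent variable is adherence, persistence, or discontinuation". The reason given is that "a previous study reported accompanying number of non-pharmacologic treatments significantly increase adherence of antidepressants".

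Table 3 (SAP 5.4) supplies the definition: "The following non-pharmacologic treatments which may affect antidepressant adherence and persistence/discontinuation will be defined using NHI procedure codes* in medical claims". Procedure codes follow, but no window. The nearest thing to timing is in SAP 2.2, where non-pharmacologic treatment may include "frequency of physician visit during acute and maintenance phase of treatment". SAP 7.2.4 uses the same kind of count as the factor of interest: "Medication compliance (adherence, discontinuation, and persistence) by the number of non-pharmacological treatments".

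The outcomes are all counted forward from the index date. For persistence, "the average length of treatment on the index drug during the first 180 day period (allowing 14 day permissible gap) will be calculated"; for discontinuation, "the percentage of discontinuation in the first 90 days from the index date (acute treatment phase) will be measured". SAP 5.1 makes these compliance measures main primary efficacy endpoints, and Protocol 9.7 compares them across the 11 drugs in raw and in matched data.

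**The concern.** A covariate in a drug comparison should be something that the drug and the outcome cannot have caused. A count of sessions accompanying treatment does not meet that test. A patient who stays on the drug and in care for 180 days has more time to accrue sessions than one who stops at day 30. The index drug may also influence how many sessions are given. The reason in 7.1 is that the count predicts adherence, not that it influences the choice of drug.

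Conditioning on such a count compares patients with similar numbers of sessions, and so partly with similar time on treatment. Some of a real difference in persistence is removed. If users of one drug receive sessions at a higher rate for unrelated reasons, equally persistent drugs will look different. The comparisons affected are primary ones.

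**Working it through.** **Is the count post-index?** Neither document says so. Four things point that way: the word for accompanying treatments in the 7.1 rationale; the treatment-phase wording in SAP 2.2; the by-number analysis in 7.2.4; and the 12-month look-back in SAP 4.1, which excludes prior depression diagnoses and study-drug claims and so should leave little earlier psychotherapy for depression to count.

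**Size.** The plan gives no figure to reproduce, and every rate below is an assumption. Take two drugs with constant stopping hazards λ of 0.008 and 0.010 per day, and let P be days on drug, capped at 180.

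- Mean P = (1 − e^(−180λ))/λ = 95.4 and 83.5 days, a true difference of −11.9 days.
- E[P²] = 2/λ² − e^(−180λ)(360/λ + 2/λ²) = 13,184 and 10,743.
- Var(P) = 13,184 − 95.4² ≈ 4,086 and 10,743 − 83.5² ≈ 3,776.
- Averages over the drugs: m = 89.4, V = 3,931, E[P²] = 11,964, squared mean 8,033.

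Let sessions follow a Poisson process at rate r per day. In a linear model of P on drug and count C, the adjusted difference is the raw difference minus β times the difference in mean C, where β = Cov(P,C)/Var(C) within drug. The share of the true difference lost is then:

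- every patient treated, only while on drug: rV/(m + rV)
- only a fraction u of patients treated: u·r·V / [m + r(11,964 − u·8,033)]
- every patient treated, half rate after stopping: 0.25rV/(90 + 0.5m + 0.25rV)

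| One session per | All, on drug only | All, half rate after stopping | 30% uptake | 10% uptake |
|---|---|---|---|---|
| 60 days | 65.5/154.9 = 42% | 16.4/151.1 = 11% | 19.7/248.7 = 8% | 6.6/275.4 = 2% |
| 30 days | 131.0/220.5 = 59% | 32.8/167.5 = 20% | 39.3/407.9 = 10% | 13.1/461.4 = 3% |
| 14 days | 280.8/370.2 = 76% | 70.2/204.9 = 34% | 84.2/771.8 = 11% | 28.1/886.6 = 3% |

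Simulation of 200,000 patients agrees for the first column: the drug coefficient goes from −12.13 to −7.07, from −11.84 to −4.88 and from −11.48 to −2.75 days. The corresponding 90-day discontinuation odds ratio moves less, from 1.38–1.39 to 1.31, 1.25 and 1.21. If only sessions in the first 30 days are counted, 1% to 4% of the persistence difference is lost; if sessions are unrelated to stopping, none is.

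A second set of assumptions (median time on drug 60 and 90 days, session rates varying between patients, 0.1 to 2 sessions per month) gives losses of 11% to 45%. They fall to 7% to 22% (0.25 to 2 sessions per month) if only the first 90 days are counted. A pre-index count that does not depend on time on drug leaves the estimate unchanged.

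**False difference.** Let both drugs have λ = 0.009 (m = 89.1, V = 3,946), with a session every 30 days on one and every 20 days on the other. With every patient treated:

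- difference in mean count = 89.1 × (1/20 − 1/30) = 1.485
- average Cov(P,C) = 3,946 × (1/30 + 1/20)/2 = 164.4
- average Var(C) = (7.36 + 14.32)/2 = 10.84, each term being rm + r²V
- false difference = −(164.4/10.84) × 1.485 = −22.5 days

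Simulated false differences at 30% and 10% uptake are about −3.3 and −0.7 days. With equal session rates there is none.

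**The case against.** **Timing and model are inferred.** Table 3 has no window, and the rationale in 7.1 describes a variable from a previous study. SAP 7.1 leaves the final variable list to analysis development. SAP 7.2.1 and 7.2.2 name only ANOVA or Kruskal-Wallis for continuous outcomes and logistic models for drug choice, so no section writes out a drug-persistence model with this covariate. The sentence could even be meant for 7.2.4. This stands in part: a reader might infer that the SAP specifies a post-index adjuster in the drug comparisons, and it does not say that. But in 7.2.4 the count is the factor of interest rather than an adjuster, the sentence sits among the methods for comparing drugs, and the covariate is stated as one that will be used.

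**Size.** A reader might also infer that drug differences are adjusted away. That needs near-universal uptake and sessions that stop with the drug, and the documents support neither. Table 3 drops the routine supportive code used for most patients, although the codes in force since January 2018, and so throughout the SAP intake period, are to be mapped by expert consensus. SAP 5.1 also ends persistence at switching, combination or augmentation, after which the patient may well remain in care. Nor do the documents give session rates by drug, so a false difference is a possibility, not a prediction.

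**Consistency and weight.** A flat contradiction with the pre-index focus of 7.1 would be too strong: that phrase concerns balance after matching, and outcome-model covariates are a separate step. Nor is non-pharmacologic treatment never a confounder; a pre-index count can be. The objectives are exploratory, SAP 3 lists no hypotheses, and Protocol 9.7 requires raw comparisons beside the matched ones. These points limit the consequences but do not make a post-index adjuster appropriate.

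**Conclusion.** The point holds conditionally. As written, the rule permits, and most naturally means, adjusting primary between-drug comparisons for a count that is partly a result of the outcome. Where sessions fall off when the drug stops, this attenuates real differences; where session rates also differ by drug, it can create false ones.

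The loss in the persistence difference ranges from 2%–3% to about 76% under the assumptions shown, and uptake and what happens to sessions after stopping decide where in that range it falls. Under a 1.5-fold session-rate ratio the false difference is about −22.5 days at full uptake but only about −3 and −1 days at 30% and 10%. The documents give none of these inputs. Adherence was not calculated separately; persistence is one of its two components. The plan should be corrected, but neither the direction nor the size of bias in the actual results can be claimed from the text.

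**What to change.** - In SAP 7.1, restrict propensity score and outcome models for between-drug comparisons to covariates measured on or before the index date.
- In Table 3, give the window for non-pharmacologic treatments. A count from the 12-month look-back may enter the between-drug models. Because that look-back can reach into 2017, settle the mapping between the old and new psychotherapy codes first.
- Use post-index non-pharmacologic treatment only as the exposure in 7.2.4. The count grows with time on treatment there too, so preferably take it from a fixed early window and follow patients from a landmark at its end, or treat it as a time-varying exposure.
- State which models the covariate sentence in 7.1 governs.

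The cost is SAP wording and some reprogramming. The claims are already in the database, and the secondary objective is kept. As SAP section 1 records that the plan was amended during data analysis, the window should be fixed without reference to the drug results.

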7.2 STATISTICAL ANALYSES

7.2.1 Study Drug Analysis in Acute Phase

- To understand the top 11 antidepressants usage among the Korean patients with depression in acute treatment phase
- Primary analysis
- Endpoints:
 - Proportion of 11 antidepressants, by age (<20, 21-64, > 65), by gender, by age and gender
 - Choice of index drug
 - Initial doses used, average daily doses of each antidepressant
 - The average length of treatment with index medication before therapy change occurs (switching, combination, augmentation, discontinuation)
 - Adherence measured by medication possession ratio and persistence during first 90 days and 180 days of treatment period, respectively
- Population: patients who meet inclusion criteria and exclusion criteria in section 4.1 and classified by the index antidepressant out of 11 top antidepressants in the Korean market (Table 2)
- Significance on continuous variables will be tested by ANOVA (if equal variance condition satisfied) or the Kruskal-Wallis H test (otherwise). Provider specialty and other patient characteristics will be used to fit antidepressant choice by multivariate logistic regression analysis of each study drug choice.
- Covariates: antidepressant class covariates such as SSRIs, SNRIs, and other ADs will be used as grouping variables.
- Missing values will be dropped from the analysis
- The role of this analysis is to provide information on study antidepressants in the acute phase of drug therapy for Korean patients with depression.

PFIZER CONFIDENTIAL

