9.7. Data analysis

The proportions and drug utilization patterns comparisons of 11 study drugs will use all the patients satisfying inclusion and exclusion criteria (raw data). Adherence, persistence, discontinuation, recurrence, and adverse outcomes comparison of 11 study drugs will use both raw data and matched data where patients will be matched on demographic and clinical characteristics. All outcome variables will be summarized *descriptively* through the tabular and graphical display of mean values, medians, ranges and standard deviations of continuous variables of interest and frequency distributions of categorical variables. Safety outcomes of treatments will be estimated from time-to-event models. The 95% confidence intervals for the estimates will be calculated and $p < 0.05$ will be considered significant. All analyses will be carried out using SAS version 9.4 which is installed on HIRA server. Analysis and reporting will be compliant with Strengthening the Reporting of Observational Studies in Epidemiology (STROBE) recommendations.

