7.2.2 Study Drug Analysis in Maintenance Phase

- To understand the top 11 antidepressants usage among the Korean patients with depression in maintenance treatment phase
- Primary analysis
- Endpoints:
 - Choice of study drug
 - Average length of new treatment maintenance
 - Average number of co-medications (e.g., atypical antipsychotics, mood stabilizer, thyroid hormone, psychostimulant) when following changes occur from initial monotherapy: switching, combination, augmentation
 - Medication compliance (adherence, discontinuation, and persistence)
 - Recurrence by each antidepressant, by compliance
 - Risk of adverse events
- Population: patients from the acute treatment phase who started maintenance treatment (after 90 days from the index date)
- Significance on continuous variables will be tested by ANOVA (if equal variance condition satisfied) or Kruskal-Wallis H test (otherwise). Provider specialty and other patient characteristics will be used to fit antidepressant choice by multivariate logistic regression analysis of each study drug choice.
- Covariates: antidepressant class covariates such as SSRIs, SNRIs, and other ADs will be used as grouping variables.
- Missing values will be dropped from the analysis
- The role of this analysis is to provide information on study antidepressants in the maintenance phase of drug therapy for Korean patients with depression.

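### For endpoints reported as averages, the SAP's unequal-variance fallback (Kruskal-Wallis) tests rank ordering, so its p-value can disagree with the means it accompanies

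*SAP*

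**What the plan says.** SAP 7.2.1 (acute phase, labelled a primary analysis) gives the rule for testing continuous variables: "ANOVA (if equal variance condition satisfied) or the Kruskal-Wallis H test (otherwise". Section 7.2.2 (maintenance phase, also primary) has the same wording, "ANOVA (if equal variance condition satisfied) or Kruskal-Wallis H test (otherwise", and the rule recurs in 7.2.3 to 7.2.5. The equal-variance check is not named.

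The continuous endpoints under this rule are mainly averages:
- 7.2.1: "The average length of treatment with index medication before therapy change occurs (switching, combination, augmentation, discontinuation", and average daily dose.
- 7.2.2: "Average length of new treatment maintenance", and the average number of co-medications.
- SAP 5.1 and Table 3 define persistence, a primary outcome, as "the average length of treatment on the index drug during the first 180 day period". MPR is a ratio and a primary outcome in its own right. Compliance, which includes persistence, is analysed in 7.2.2 and 7.2.4.

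SAP 7.1 adds that "Means, medians, and standard deviations will be provided for continuous variables". Protocol 9.7 sets the inferential standard: "The 95% confidence intervals for the estimates will be calculated and $p < 0.05$ will be considered significant". SAP section 3 (hypotheses and decision rules) is marked not applicable.

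**The concern.** Kruskal-Wallis asks whether patients on one drug tend to rank above patients on another. That becomes a statement about means or medians only if the groups share a distributional shape. The SAP turns to the test exactly when unequal variances show that they do not. It names no test of means that allows unequal variances.

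Persistence is a likely place for this to matter. It is bounded at 180 days and ends at any switch, combination, augmentation or discontinuation. Early stopping and a pile-up at 180 days are therefore plausible, and their balance may differ by drug. The risk is a primary table that prints mean days by drug next to a p-value that does not test those means.

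**Working it through.** **Nothing to reproduce.** The documents give no sample size, power, SD or distribution for these comparisons. The check is therefore a simulation under stated assumptions.

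**Likely cohort size (assumption).** Protocol 9.5 cites 752,190 new users over 60 months. Pro rata to the 18-month intake: 752,190 × 18/60 = 225,657, and 225,657/11 ≈ 20,514 per drug if evenly split. The age cap and exclusions would change this. At such sizes an equal-variance test rejects for small differences, so the fallback would probably be the usual path.

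**Simulation 1: equal means of 90 days.** Rule: median-centred Levene at 0.05, then ANOVA or Kruskal-Wallis. There were 1,000 runs at 100 and 500 per drug and 300 runs at 2,000. Monte Carlo error at 5% with 300 runs is ±1.96 × √(0.05 × 0.95/300) ≈ ±2.5 points. Assumed shapes:
- S = 180 × Beta(2,2): median 90, SD 40.
- R = 37.5% at the 180-day cap, the rest 180 × Beta(1.2,4.8) with mean 36. Mean 0.375 × 180 + 0.625 × 36 = 90; median 58, SD 73.
- U = 180 × Beta(0.5,0.5): symmetric, SD 64.

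Rejection at nominal 5%, for 100 / 500 / 2,000 per drug:

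| Setting | SAP rule | Welch |
|---|---|---|
| 11 drugs, 6 S and 5 R | 27.9% / 92.1% / 100% | 4.7% / 4.0% / 6.0% |
| 11 drugs, 10 S and 1 R | 13.0% / 40.7% / 95.0% | 5.5% / 5.1% / 5.0% |
| 11 drugs, 6 S and 5 U (symmetric) | 6.7% / 6.4% / 7.0% | 5.6% / 6.2% / 6.3% |
| 11 drugs, all R (identical) | 4.6% / 3.7% / 3.7% | 5.3% / 5.0% / 4.3% |

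Levene rejected in every run of the first three settings.

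**Simulation 2: equal means of 80 days.** Beta shapes on 0 to 180, 11 drugs in size ratio 5:3:2:2:1:1:1:1:1:0.5:0.5, SDs evenly spaced and assigned in both orders.
- SD 45 to 71: Kruskal-Wallis rejected 10–26% at total n = 3,600, 36–47% at 9,000, 74–79% at 18,000 and 100% at 90,000. Welch: 4–7%.
- SD 57 to 63: Kruskal-Wallis rejected 23–28% at 90,000. Welch: 3–5%.

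**The opposite error.** With S against R, P(S > R) = 0.5386. Capped values always exceed S, so for the uncapped part X, P(S > X) = 0.5386/0.625 = 0.8618. The rank comparison balances when (1 − c) × 0.8618 = 0.5, giving a capped share c = 0.4198. The mean of R is then 0.4198 × 180 + 0.5802 × 36 ≈ 96.4 days against 90 for S. A true difference of about 6.4 days gives the rank test nothing to detect, and a larger sample does not help.

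**What a test of means does at this size.** Take SD 60 days (assumption), 20,514 per drug, and true drug means varying with an SD of only 0.5 day. The noncentrality is 11 × 20,514 × 0.5²/60² = 15.67, and power with 10 numerator degrees of freedom is about 78%. At 0.75 day it is 99.5%. The 95% interval for one between-drug difference would be ±1.96 × 60 × √(2/20,514) ≈ ±1.2 days.

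**The case against.** The strongest objection is that correcting the test may seldom change a significance statement. In a cohort this large, Welch ANOVA would also give p < 0.05 for differences of under a day. This stands, and it is why the remedy must put mean differences and intervals first. Protocol 9.7 already promises 95% confidence intervals for estimates, but SAP 7.2 does not carry them to these comparisons.

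Second, the work is exploratory: section 3 is not applicable, and 7.2.1 and 7.2.2 are there to provide information. This lowers the severity. It does not make a stated significance test fit its endpoint.

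Third, medians are planned beside means, and SAP 7.1 adds propensity score matching and weighting and covariate adjustment. But no endpoint is defined as a median, and with differing shapes Kruskal-Wallis does not test medians either. Section 7.1 offers the t-test and chi-square test as examples and names no model for a continuous outcome, so 7.2 remains the specific rule.

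Fourth, the simulated shapes are assumptions. This also stands: with symmetric shapes the excess is about two points. A reader might infer that drugs with equal average persistence will be declared different. The documents do not support that, because they give no distribution for any drug and no reason to expect exactly equal means.

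**Conclusion.** The mismatch is real in 7.2.1, 7.2.2 and the persistence part of 7.2.4. When variances differ, the planned p-value for an average tests rank ordering. It can be significant with equal means, or silent when means differ by several days. How often is unknown: the simulated rejection rates with equal means run from near nominal (symmetric shapes) to 100% (strongly different skewness, large n), and they are illustrative only.

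A reader might extend the point to all of 7.2 or to adherence in general. The documents do not support that. Sections 7.2.3 and 7.2.5 list only proportions and choice of drug, so the rule has no listed continuous endpoint there. Adherence classified by the thresholds on MPR and persistence is binary. Nor does this amount to a failed primary hypothesis test, since none is specified. Severity is minor to moderate.

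**What to change.** In SAP 7.2.1, 7.2.2 and the persistence part of 7.2.4:
1. Replace the two-way rule, for endpoints reported as averages, with Welch ANOVA or linear regression with robust standard errors, without a preliminary equal-variance test. The regression form can also carry the covariates or propensity weights of 7.1.
2. Make between-drug mean differences with 95% confidence intervals the main result, and read importance from their size in days, dose or ratio units, not from p < 0.05.
3. If Kruskal-Wallis is kept, label it secondary and describe it as a comparison of rank ordering, not of means or medians.
4. Delete the rule from 7.2.3 and 7.2.5, or name the continuous variable it is meant for.

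The cost is a few lines of SAP text and a small change to the SAS programs; no new data are needed. SAP section 1 records that the plan was amended during data analysis, so the change should be dated and should state whether these comparisons had already been seen.
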